3. EXPERIMENTAL PROCEDURES AND DATA ACQUISITION

3.1. BLOOD SAMPLES

In patients with suspicion of telomeropathy, Flow-FISH analyses are already used for the diagnosis in routine. These standard of care procedures will therefore not be associated with any additional cost.

Blood tests will be performed by nurses at the blood collection center of the CUSL. One EDTA tube of 7.5 ml is sufficient for Flow-FISH. Blood tests will be performed while the patient is at the clinic and will not require a supplementary consultation.

We will measure leukocyte telomere length using a validated Flow-FISH technique, developed by Prof [name] (UCL), and available at CUSL.

Blood sample for Flow-Fish analysis is performed as standard of care procedure for the patients involved in the study. Therefore, these analyses will not be associated to additional costs, neither in term of material of personal.

A Figure is enclosed to this document to summarize experimental procedures and samples flow.

Residual material will be stored in the UCLouvain biobank, at Prof. [name]' lab. They will be kept for 10 years and then will be destroyed.

3.2. NASAL BRUSHINGS

The nasal brushings will be performed by Prof. [name] or [name], trained ENT specialists, during their scientific time. For patients and controls recruited among patients from the clinic, nasal brushings will be performed while these subjects are at the clinic for their standard cares. For controls recruited outside the clinic, the nasal brushing will require a specific study consultation.

A local vasoconstrictor (Xylometazolin, 1mg/ml) will be applied at the level of the head of the inferior turbinate with the use of a nasal tampon to facilitate the visibility and the access to the olfactory cleft. Each nostril will be assessed, using a 30° rigid endoscope of 4mm (Karl Storz[®], Tuttlingen, Germany), in order to identify the nostril having the most accessible olfactory cleft. This nostril will be chosen to receive the brushing. A sterile disposable cytology brush (i.e. FLOQSwabs, Copan[®], Italy) will be gently rolled on the mucosal surface, at the level of the head of the middle turbinate, as described previously (Orrù et al., 2014). Two brushings will be done for each subject. The brush will then be immerged in a conical centrifuge tube containing DMEM-F12 medium supplemented with GlutaMAX. Cellular material will then be dissociated from the brush using disposable micropipette tips.

In the patients group, cellular material will be split into three parts for specific processing. A first part will be cultured (Prof [name]' lab, de Duve Institute) (Endpoint #2), a second one will be processed by Cytospin for future stainings (Endpoint #1) (Prof [name]' lab, de Duve Institute) and the last part will be kept frozen and further used for whole exome sequencing (Endpoint #1), if the suspicion of telomeropathy has been confirmed. This latter step will be performed at the laboratory of genetics of CUSL (Prof. [name]) In the control group, cellular material will be exclusively used for the staining evaluating the degree of senescence and damages to telomeres.

A Figure is enclosed to this document to summarize experimental procedures and samples flow.

Figure summarizing experimental procedures and samples flow in patients (A) and controls (B)

3.3. SNIFFIN' STICKS TEST

Olfactory function will be evaluated in the department of Otorhinolaryngology of CUSL (Prof. [name]).

For patients and controls recruited among patients from the clinic, olfactory tests will be performed while these subjects are at the clinic for their standard cares. For controls recruited outside the clinic, olfactory testing will require a specific study consultation (at the same time than the nasal brushing).

For adult participants, we will use the Sniffin' Sticks test which is a validated psychophysical testing method (Hummel et al. 2007). Sniffin' Sticks test is based on pen-like odor dispensing devices that will be presented to the patients. The extended version of this test will be used and consists of three tests of olfactory function, namely tests for odor threshold, odor discrimination and odor identification. Odor threshold for n-butanol will be assessed using a single-staircase, three alternative forced choice procedure. Odor discrimination will be assessed using again a three alternative forced choice procedure. Triplets of pens will be presented to the patients, with two containing the same odorant and one a different odorant. Odor identification will be assessed for 16 common odors using a multiple-choice identification from lists of four descriptors each. In order to quantify olfactory function, results from the three subtests will be presented as a composite "TDI score" (/48) which is the sum of the results obtained for each subtest: threshold (/16), discrimination (/16), identification (/16). TDI score will be used to classify patients in three categories: normosmic, hyposmic or anosmic.

For the pediatric population, we will use an adapted version of the Sniffin' Sticks test, the Sniffin' Kids test. This test is a 14-item odor identification test and has been validated in children between 6-17 years of age (Schriever et al. 2014). Therefore, considering Endpoint #3, olfactory function will be assessed only in participants >6 years old. Olfactory function will be assessed during the hospitalization, before the general anesthesia.

4. RECRUITMENT OF PARTICIPANTS

Patients with a suspicion of telomeropathy (i.e. idiopathic pulmonary fibrosis, medullar aplasia, myelodysplasia, unexplained liver cirrhosis, unexplained liver regenerative nodular hyperplasia) will be recruited through pneumology (Prof. [name]), adult hematology (Prof. [name]), pediatric hematology (Prof. [name]) and adult hepathology (Prof. [name]) consultations.

Adult healthy controls will be recruited through the consultation of otorhinolaryngology (Prof. [name], Prof. [name]) or through advertising. Notably, pediatric controls will be recruited from children patients planned for elective otorhinolaryngologic surgery under general anesthesia.

The physician in charge of the patients will briefly outline the objectives of the study to the potential participants and/or their parents. With their permission, the potential participants will then be contacted by one of the investigators who will provide detailed explanation of the project's objectives. If interested, the patients and/or their parents will receive a letter of invitation and information sheet will be given to the putative participants. They will be free to contact us

should they require further clarification or information concerning inclusion and exclusion criteria. It will be clearly explained that accepting or refusing to participate will have absolutely no impact on present or future care. Subject and/or their parents will benefit from at least 24h and enough time to agree to participate or not to the study.

If the subject and/or his parents agree to participate to the study, an appointment will be fixed, if possible, on the same day that a routine medical visit to the CUSL. Written informed consent will be collected that day by the principal investigator or one of the medical co-investigator. After giving their written informed consent, subjects will be enrolled in the study. The informed consent sheet will list the specific experimental procedures and tests required to conduct the study, as well as the maximum duration of the experiment/testing.

5. INFORMED CONSENT

Before any screening or study-specific procedure is performed, the subject will be asked to sign and date the subject information sheet and accompanying informed consent form. Importantly, since the present study involves genetic testing in patients, patients will be explicitly informed that they are able to participate to the study although refusing to take part to the genetic testing. A specific informed consent form for genetic testing will be signed as well. The informed consent will also mention if volunteers will have access or not to their own results. Specifically, for genetic analysis, we will ask the patients whether they want to be informed about the results or not.

For minor subjects, both parents will be asked to sign and date a specific information sheet and accompanying informed consent. Pediatric patients older than 6 years will also be asked whether they agree to participate to this study. Pediatric patients will receive adapted information, both through oral explanations and through age-adapted informed consent.

Therefore, we will propose specific informed consents to (1) adult patients, (2) adult controls, (3) patients' parents, (4) controls' parents, (5) 6-11 years old patients, (6) 6-11 years old controls, (7) 12-14 years old patients, (8) 12-14 years old controls, (9) 15-17 years old patients, (10) 15-17 years old controls.

6. PRE-STUDY SCREENING

After signing the informed contents, investigators will screen the subject to ensure the eligibility of the subject.

Demographics. The date of birth and gender of the subject will be recorded.

Medical and surgical history. Subjects will be asked whether or not they suffer from any known disease, notably from sinonasal disorders, psychiatric or neurological disease, history of olfactory dysfunction (i.e. following upper respiratory tract infection, head trauma). We will also record medical and surgical ENT history. Additional questions will be asked to ensure correct screening for inclusion and exclusion criteria, as detailed in section 7. *Physical Examination*. Subjects will undergo a rhinological endoscopic examination to assess olfactory cleft, notably to rule out any skull base abnormality such as meningocele or abnormalities that may lead to bleeding.

At the end of the screening visit, and taking into consideration the inclusion and exclusion criteria, the eligibility of the subject will be decided.

7. SELECTION AND WITHDRAWAL OF VOLUNTEERS

7.1. Inclusion and exclusion criteria

Endpoints #1 and #2

Study population			Inclusion criteria	Exclusion criteria	
Adults years)	(>18	Patients	 Having a suspicion of or a confirmed telomeropathy Ability to provide written informed consent 	 No access to the olfactory cleft Abnormal endoscopic finding (i.e. meningocele, vascular ectasia) 	
		Controls	- Ability to provide written informed consent	 No access to the olfactory cleft Abnormal endoscopic finding (i.e. meningocele, vascular ectasia) 	
Children years)	(<18	Patients	- Written informed consent obtained from the parents and participant if she/he is older than 6 years old	 No access to the olfactory cleft Abnormal endoscopic finding (i.e. meningocele, vascular ectasia) 	

Controls	- Written	- No access to
	informed	the olfactory
	consent	cleft
	obtained from	- Abnormal
	the parents	endoscopic
	and	finding (i.e.
	participant if	meningocele,
	she/he is	vascular
	older than 6	ectasia)
	years old	

Endpoint #3

	dy population	Inclusion criteria	Exclusion criteria	
Adults	Patients	 Having a suspicion of or a confirmed telomeropathy Ability to provide written informed consent 	neurological or psychiatric disorder known	
	Controls	- Ability to provide written informed consent	 History of neurological or psychiatric disorder known to interfere with olfactory function History of olfactory trouble (postinfectious, posttraumatic, toxic) or chronic rhinosinusitis 	
Children	Patients	 Age: 6-18 Written informed consent obtained from the parents and participant 		

				posttraumatic, toxic) or chronic rhinosinusitis
Controls	-	Age: 6-18 Written informed consent obtained from the parents and participant	-	History of neurological or psychiatric disorder known to interfere with olfactory function History of olfactory trouble (postinfectious, posttraumatic, toxic) or chronic rhinosinusitis

7.2. Discontinuation criteria

The subject may be excluded for the reasons given in section 7.1 of this protocol. The excluded subjects will be replaced.

Participants and/or their parents will be informed of the fact that they have the right to withdraw from the experiment at any time and for any reason, without prejudice, and without being obliged to give the reasons for doing so.

In the interest of the subject's health and well-being, the investigator may withdraw the subject at any time. In addition, the subject may be withdrawn for any of the following reasons: administrative decision by the investigator, ineligibility, subject non-compliance with study requirements, and occurrence of any adverse event which results in the inability to continue to comply with study procedures.

The reason for withdrawal will be recorded. If the subject is withdrawn due to an adverse event, the investigator will arrange for follow-up visits or telephone calls until the adverse event has resolved or stabilized.

8. SAFETY

8.1. Adverse event

An adverse event is defined here as a harmful and unintended occurrence in a subject participating to the study. All adverse events will be reported from the time a signed and dated informed consent form is obtained, until completion of the last study-related procedure.

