8.4. Reporting procedures for all adverse events

All adverse events occurring during the study observed by the investigator or reported by the subject, whether or not attributed to the study, will be recorded. The following information will be assigned by the investigator: description, date of onset and resolution, severity, assessment of relatedness to the experiment, and action taken. The investigator may be asked to provide follow-up information. All related adverse events that result in a subject's withdrawal from the experiment will be followed up until a satisfactorily resolution occurs.

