8.5. Serious adverse event reporting procedures

A serious adverse event occurring to a research participant will be reported to the Ethics Committee that gave a favorable opinion of the study. Reports of related and unexpected serious adverse events will be submitted within 15 days after becoming aware of the event.

All serious adverse events that have not resolved by the end of the study, or that have not resolved upon discontinuation of the subject's participation in the study will be followed until any of the following occurs: (1) the event resolves, (2) the event stabilizes, (3) the event returns to baseline, if a baseline value is available, (4) the event can be attributed to agents other than the experiment, (5) when it becomes unlikely that any additional information can be obtained (subject or healthcare practitioner refusal to provide additional information, lost to follow-up after demonstration of due diligence with follow-up efforts).

Any event requiring hospitalization that occurs during the course of a subject's participation in a clinical study will be reported as a serious adverse event except hospitalizations for (1) social reasons in absence of an adverse event, (2) surgery or procedures planned before entry into the study, (3) clinic protocol procedures.

All of the medical investigators of this project are medical practitioners registered to l'Ordre des Médecins/Orde der Artsen. It will be left to their judgment to decide whether or not an adverse event is of sufficient severity to require the subject's removal from the study. A subject may also voluntarily withdraw from the study due to what he or she perceives as an intolerable adverse event.

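### Section 8.2 makes unexpectedness part of seriousness, in conflict with 8.5, and the adverse-event window in 8.1 can close as the brushing ends

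*Combined protocol and SAP*

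**What the plan says.** **Reporting window.** Section 8.1 collects adverse events from signed consent "until completion of the last study-related procedure". It does not name that procedure and adds no interval after it. Section 8.4 records "All adverse events occurring during the study observed by the investigator or reported by the subject". Section 8.5 refers to the end of the study and to the subject's participation. None of these periods is defined.

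**Follow-up.** Section 7.2 states: "If the subject is withdrawn due to an adverse event, the investigator will arrange for follow-up visits or telephone calls". Under 8.4, related events leading to a subject's "withdrawal from the experiment will be followed up until a satisfactorily resolution occurs". Section 8.5 follows "All serious adverse events that have not resolved by the end of the study", which includes subjects who completed.

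**Seriousness.** Section 8.2 requires an occurrence to be unexpected and to have one of four outcomes: death, threat to life, hospitalisation or a prolonged stay, or lasting or significant disability. Section 8.5 begins: "A serious adverse event occurring to a research participant will be reported to the Ethics Committee". It continues: "Reports of related and unexpected serious adverse events will be submitted within 15 days after becoming aware of the event". It then says that any event needing hospitalisation during a subject's participation "in a clinical study will be reported as a serious adverse event except hospitalizations for" three listed reasons: social reasons, procedures planned before entry, and protocol procedures.

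**Foreseen harms.** Section 8.3 anticipates slight bleeding where the mucosa is fragile, regards severe bleeding as extremely rare, and provides for measures if a subject complains of a smell problem.

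**The concern.** Seriousness is normally a matter of outcome, and expectedness a separate judgement that decides how fast to report. Section 8.2 merges the two and 8.5 keeps them apart. An investigator who follows 8.2 could leave a foreseen but grave event out of Ethics Committee reporting and follow-up, while one who follows 8.5 would include it if it led to hospitalisation. Many of these patients have severe underlying disease (2.2.1), so grave events that someone could call foreseeable are not far-fetched.

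The window matters because the harms named in 8.3 need not appear while the subject is still in the room. If reporting stops as the brush is withdrawn, the safety record covers the procedure and not its aftermath. Section 2.2.2 presents brushing as a possible non-invasive clinical tool. That case rests on detection of telomere damage, senescence and mutations, but these brushings will also be the study's own experience of how the procedure is tolerated.

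**Working it through.** The plan states no figure on this point, so the check is mainly a comparison of the text.

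**Step 1: seriousness.** Let O mean that an event has one of the four outcomes in 8.2, U that it is unexpected, and R that it is related.

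- 8.2: serious = O and U.
- 8.5, hospitalisation rule: serious = requires hospitalisation and is none of the three exceptions. U is not required.
- 8.5, 15-day rule: R and U and serious.

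| Event | Under 8.2 | Under 8.5 |
|---|---|---|
| Foreseen, requires hospitalisation, no exception applies | Not serious | Serious |
| Foreseen, fatal, life-threatening or disabling, no hospitalisation | Not serious | Not addressed, so 8.2 decides: not serious |
| Unexpected, fatal, life-threatening or disabling | Serious | Serious through 8.2 |

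The first row is a direct conflict, and the second is a gap caused by the wording of 8.2. The separate U in the 15-day rule would be redundant if 8.2 were meant as written, so 8.5 presupposes that a serious event can be expected.

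The 15-day set does not change. With 8.2 as written it is R and U and (O and U), which reduces to R and U and O. With an outcome-only definition it is R and U and O directly. What changes is the general report to the Ethics Committee and the follow-up of unresolved serious events.

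**Step 2: the window.** Three readings of the last procedure are possible.

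- *Per subject, the last procedure done on the person.* This is the natural reading, because 8.1 starts at that subject's consent. In adults the last procedure is the brushing or the smell test; their order is not given, and controls from outside the clinic have both in one consultation (3.3). In children the smell test precedes anaesthesia (3.3) and sampling takes place during it (8.3; 2.2.2 says this is done where possible for paediatric patients). The window can then close while the child is anaesthetised.
- *Per subject, including laboratory work on the sample.* The window would run longer, but by an amount unrelated to the subject's exposure.
- *Study-wide.* Early subjects would be covered for a long time and the last subject hardly at all. A later event would be recorded under 8.4 if someone observed or reported it.

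On the first reading, take a non-serious bleed or smell complaint first noticed afterwards. The follow-up in 7.2 and 8.4 depends on withdrawal, and a subject who has finished has little left to withdraw from. The follow-up in 8.5 requires a serious event that is already known. No follow-up rule reaches this event, and 8.1 places it outside reporting.

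**Step 3: exposure.** 150 patients + 100 controls = 250 subjects brushed. The documents give no rate or onset time for harms of olfactory-cleft brushing. The nasopharyngeal-swab study cited in 8.3 had 8 complications in 643,284 patients, 4 of them bleeding:

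- all complications: 8 / 643,284 × 250 = 0.0031 expected in 250;
- bleeding only: 4 / 643,284 × 250 = 0.0016 expected in 250.

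That source concerns another site, is retrospective, and its 8 complications (4 bleeding, 4 foreign body) include no smell complaint. It does not give the rate of the harms at issue.

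**The case against.** The other side has a good deal to say. Section 8.1 does state an end point, and 8.4 records everything observed or reported, whether or not attributed to the study. Subjects are screened by endoscopy, trained specialists do the brushing, and measures are foreseen for bleeding and smell complaints. Serious harm is expected to be rare, no endpoint concerns safety, and the study has one centre. The consent forms were not available and may ask subjects to report later problems. All of this stands, and it keeps the severity down. It does not remove the conflict over expectedness, and it does not say which procedure closes the window.

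A reader might infer four stronger points that the documents do not support.

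- *That reporting has no defined end.* An end is stated; it is imprecise and can fall very early.
- *That 8.5 contradicts 8.2 on the three exceptions and on prolonged stays.* Section 8.5 is a reporting section and gives no second full definition. Section 8.2 already covers prolongation, and 8.5's silence on it is a gap. The exceptions qualify reporting and are better stated once, but they are not a contradiction.
- *That urgent reports would be missed because of the expectedness conflict.* Step 1 shows that the 15-day set is unaffected.
- *That the absence of a scheduled contact after brushing is itself an error.* The protocol indeed describes none that would look for new events, but it promises none either. Adding one is a design preference.

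**Conclusion.** Two rules are defective as written. The expectedness condition in 8.2 conflicts with 8.5 and leaves a foreseeable fatal, life-threatening or disabling event outside the definition of serious. The window in 8.1, on its natural per-subject reading, can end with the brushing and so exclude later harms that 8.3 itself names.

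Severity is low to moderate. No endpoint is affected. The consequences are confined to general Ethics Committee reporting and follow-up of foreseen grave events, and to the completeness of the tolerability record. No count of missed events can be given, and the swab figures neither establish nor exclude a problem.

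The conclusion on the window assumes the per-subject reading. On a study-wide reading later events can still be recorded, but only if observed or volunteered. The conclusion on 8.2 assumes that some grave events could be judged expected; the protocol gives no reference list for that judgement beyond the harms discussed in 8.3. Both conclusions concern the protocol text only.

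**What to change.** 1. **8.2 and 8.5.** Delete the expectedness condition from 8.2 so that seriousness depends on outcome alone. Keep expectedness for the 15-day rule in 8.5. Have 8.5 refer to the 8.2 definition, including prolongation of stay, and state the three hospitalisation exceptions once.
2. **8.1 and 8.4.** Define the window per subject, from consent to a fixed interval after the brushing, with the interval set by the sponsor and the ethics committee. Use the same window in 8.4.
3. **Follow-up.** Keep the 8.5 follow-up of unresolved serious events.
4. **Children.** Record whether an event is attributed to the concurrent surgery or procedure, since a longer window will also pick up its effects.
5. **Optional.** Make one brief structured contact at the end of the window. At an assumed 5 to 10 minutes each, 250 contacts take 250 × 5 / 60 = 20.8 to 250 × 10 / 60 = 41.7 staff hours. Items 1 to 4 do not depend on it.

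The cost is an ethics amendment (11.3), possible updates to some of the ten consent versions listed in section 5, and a few more recorded events. No invasive procedure is added.
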